# 9.2 Secondary Outcomes and Analyses

Comparisons of the primary study outcomes will be made for those with vs. without diabetes at study entry, BMI <35 kg/m2 vs. ≥35 kg/m2 at study entry, by race/ethnicity and sex, by baseline HbA1c and β-cell function, and by categorical groups of various biomarkers.

Analysis of covariance will be used to compare the metformin and gastric band groups for additional continuous variables of interest at both the 12-month and 24-month time points relative to the start of the interventions. As for the primary outcomes, all analyses will be adjusted for the baseline value of each endpoint.

An important secondary analysis of this study is to determine whether ß- and  $\alpha$ -cell function from OGTT and fasting samples are sufficiently well correlated with more robust assessments of ß- and  $\alpha$ -cell function obtained from the hyperglycemic clamp to validate their use in large clinical trials. For these analyses, Pearson and non-parametric Spearman correlations of simple versus sophisticated measures of ß- and  $\alpha$ -cell function will be computed.

To examine biomarker associations with glucose metabolism, Pearson and non-parametric Spearman correlations of each biomarker with ß- and  $\alpha$ - cell function, insulin sensitivity and glucose tolerance measures will be determined. In addition, multiple linear regression models

will be developed to predict measures of glucose metabolism with the most informative biomarker sets.

Other planned secondary analyses will examine relationships between exposure variables such as body weight and fat, insulin resistance; circulating adipokines and fat metabolites, and glucose levels and primary and secondary β-cell outcomes within and across treatment groups.

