#### **3.3.2 OGTT-derived** ß-cell measures

- a. Early insulin response to oral glucose (insulinogenic index:  $\Delta$  insulin from 0-30 minutes/ $\Delta$  glucose from 0-30 minutes [ $\Delta$ I/ $\Delta$ G])
- b. Early C-peptide response to oral glucose (analogous to (a))
- c. Oral disposition index (DIo; insulinogenic index adjusted for insulin sensitivity)
- d. Modeled parameters of ß-cell function (ß-cell glucose sensitivity, rate sensitivity and potentiation factor; static, dynamic, and total ß-cell glucose sensitivity)
- e. Ratios of incremental insulin/glucose (iAUCins/iAUCg) and C-peptide/glucose (iAUCcp/iAUCg) responses from 0-120 minutes
- f. Incremental glucose (iAUCg) response as a measure of glucose tolerance
- g. 2-hour glucose

- h. GLP-1 total and incremental response to oral glucose load (samples will be collected, and measured for this analysis if funding allows)
- **3.3.3** Fasting measures of glycemia and β-cell function
  - a. Glucose
  - b. Proinsulin/insulin ratio
  - c. HOMA %B (using the Oxford calculator)
  - d. HbA1c

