## 4.4 Screening

Screening will take place on the Clinical Trials Unit (CTU) at USC. Individuals will have a history and physical exam directed at study inclusion/exclusion criteria, will provide blood for clinical laboratory screening, and will have plasma glucose measured before and two hours after 75g oral glucose challenge. Qualified individuals will be asked to return for baseline testing and randomization.

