## 4.5 Randomization

Individuals who complete baseline testing (described below, section 6.2) will be randomized 1:1 to banding or metformin using permuted block randomization stratified by gender, BMI (30-35 vs. 35-40 kg/m^2) and diabetes (no vs. yes when IDE approved) to minimize skewing. Individuals assigned to metformin will be given study medications and instructions at the end of the second baseline visit, to begin treatment the following day. Individuals assigned to gastric banding will be scheduled for pre-operative screening with the goal of having them undergo operation within two weeks.

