# **6 DATA COLLECTION**

## 6.1 Pre-screening and Screening Eligibility Measurements

*Prescreening*: Prescreening for potential eligibility is done using clinical databases at Kaiser Permanente Southern California and the Ambulatory Care Network of Los Angeles County. Participants are eligible to continue screening procedures if they have an A1C within six months that was 5.8-7.0% and are 20-65 years old with BMI 30-40 kg/m2. For Kaiser, letters are sent to potential participants describing the purpose of the study and providing individuals the opportunity to opt in to be contacted. For the ACN, potential participants are contacted directly. In both cases, a study recruiter interviews potential subjects by phone to determine potential eligibility and interest in the study.

*Screening*: Participants who meet pre-screening eligibility criteria are invited to the USC Clinical Trials Unit to provide informed consent and complete screening, including a directed history and physical exam, clinical laboratory tests, and a 2-hr, 75 g OGTT.

Table 6.1: Data Collection during Screening							
STEP	TEST / PROCEDURE	COMMENTS					
1) Pre-screening	HbA1C, BMI (EHR), age, ICD-9 codes	Contact if A1C 5.8-7.0%, age 20- 65, BMI 30-40 kg/m 					
	Phone Screening questionnaire	Initial review of eligibility					
2) Screening	fasting and 2-hr glucose (75 gram OGTT; measured at central lab), A1C	Eligibility: fasting glucose >90 mg/dl; 2-h glucose ≥140 mg/dl, AIC <7.0%					
	Clinical eligibility labs (local clinical lab)* Targeted history and physical exam, Beck Depression Inventory	Laboratory eligibility criteria Eligibility evaluation					

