# 6.2 Main Study Procedures

The timing of major study procedures is illustrated in the Figure 3, Section 3 above. Data to determine main study outcomes using hyperglycemic clamp procedures will be obtained at baseline and study end, which will be defined as either the end of 24 months after initiation of metformin or placement of gastric band, or at the time of treatment failure (A1C >8.0% on two successive visits). Data for secondary analyses will be determined at other study visits. Blood and urine samples will be collected for planned measures and extra blood and urine samples will be stored for future analyses. Further details on these measures are provided below, and are summarized in Table 6.2.

	Baseline	2-mo	4-mo	6-mo	8-mo	10-mo	12-mo	15-mo	18-mo	21-mo	24 mo
Exam	X	X	Х	Х	Х	Х	Х	Х	X	Х	Х
OGTT	X						Х				Х
Hyperglycic Clamp	X						Х				Х
DEXA	X						Х				Х
MRI	X						Х				Х
A1C	X		Х	Х		Х	X		X		Х
Fasting/Biomarkers	X			Х			Х		X		Х
Band Questionnaires	X			Х			Х		X		Х
Sleep Questionnaires	X										
Clinical Labs-1	X			Х			Х		X		Х
Clinical Labs-2				Х			Х		X		Х

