## 6.2.2 Oral Glucose Tolerance Test (OGTT)

Participants will come to the clinical research testing facility in the morning following a 10-12 hour overnight fast. They will drink 75 grams of an oral glucose solution (centrally provided from a single manufacturer) over ≤5 minutes. Blood samples will be obtained at -10, -5, 10, 20, 30, 60, 90, 120, 150 and 180 min relative to glucose ingestion. OGTT procedures will be performed at baseline and 12 and 24 months after initiation of metformin or placement of gastric bands.

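### 2-hour glucose is measured twice before randomisation, but Section 9.2 adjusts only for an undefined baseline value; adding the screening value would give a small, nearly free gain in precision

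*Combined protocol and SAP*

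**What the plan says.** Section 9.2 plans ANCOVA comparisons of metformin and banding at 12 and 24 months and fixes the covariate in one sentence: "As for the primary outcomes, all analyses will be adjusted for the baseline value of each endpoint". The term is in the singular and is not defined further. The screening result is neither included nor excluded.

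The endpoint list in Section 3.3.2 contains "g. 2-hour glucose". Table 6.1 has it measured at screening: "fasting and 2-hr glucose (75 gram OGTT; measured at central lab), A1C". The same table selects on it: "Eligibility: fasting glucose >90 mg/dl; 2-h glucose ≥140 mg/dl". Section 4.4 makes baseline a later occasion: "Qualified individuals will be asked to return for baseline testing and randomization". Section 6.2.2 then schedules a fuller test: "OGTT procedures will be performed at baseline and 12 and 24 months after initiation of metformin or placement of gastric bands". That test has ten samples, from -10 to 180 minutes, whereas screening takes glucose only fasting and at two hours. Section 4.5 places randomisation after both: "Individuals who complete baseline testing (described below, section 6.2) will be randomized 1:1 to banding or metformin".

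No section gives the screening glucose any use beyond eligibility.

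**The concern.** A single 2-hour glucose value mixes a person's usual level with day-to-day variation. As a covariate it therefore removes less outcome variance than two values would. Both values precede allocation, so using both leaves the randomised comparison unbiased, even though the screening value is truncated by the eligibility limit.

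What is at stake is width of confidence intervals. Section 9.3 limits surgery to 44 participants, and 44 x 0.9 x 0.9 = 35.6, so about 35 per arm are expected to complete. Section 5.4 says the budget rules out large increases in enrolment. Extra precision has to come mainly from the analysis.

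**Working it through.** **1. The plan's own figures.** With 35 per arm and two-sided alpha 0.05, a t-test (68 df) has 80.1% power for an effect of 0.68 SD; Section 9.3 states 80%. With baseline adjustment at r = 0.5 the residual SD is sqrt(1 - 0.25) = 0.866 (67 df). Power at 0.68 SD is then 89.9% (stated 89%) and the effect detectable with 80% power is 0.588 SD (stated 0.59). The figures reproduce. The r of 0.5 is given for the primary outcomes; none is given for 2-hour glucose.

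**2. Closed form, no selection.** Let r be the correlation of either pre-randomisation value with follow-up, and rho the correlation between the two values (assumed; not in the documents). Residual variance is 1 - r² with one value and 1 - 2r²/(1 + rho) with two. At r = 0.5:

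| rho | One value | Two values | Reduction |
|---|---|---|---|
| 0.5 | 0.750 | 1 - 0.5/1.5 = 0.667 | 11.1% |
| 0.8 | 0.750 | 1 - 0.5/1.8 = 0.722 | 3.7% |
| 0.9 | 0.750 | 1 - 0.5/1.9 = 0.737 | 1.8% |

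If eligibility keeps only the upper 50-80% of screening values (assumed), these fall to 5.1-7.5%, 2.3-3.0% and 1.3-1.5%.

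**3. Simulation on the mg/dl scale.** All inputs except the 140 mg/dl limit are assumptions: true 2-hour glucose with mean 155 and SD 35; independent error SD 20-35 at each measurement; SD of true individual change 15-35; people kept only if the screening value is at least 140. The resulting correlation of baseline with follow-up is 0.33-0.59. Reduction = 1 - (1 - R² with both)/(1 - R² with baseline only).

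| Setting | R², baseline only | R², both | Reduction in residual variance |
|---|---|---|---|
| Error SD 20, change SD 15 | 0.344 | 0.407 | 1 - 0.593/0.656 = 9.6% |
| Error SD 35, change SD 35 | 0.109 | 0.140 | 1 - 0.860/0.891 = 3.5% |

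The standard error falls by 1 - sqrt(0.904) = 4.9% and 1 - sqrt(0.965) = 1.8%. Against 70 completers this equals 70/0.904 = 77.4 and 70/0.965 = 72.5, or about 3 to 7 more. The mean of the two values did as well as entering both.

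**4. With a diabetes stratum in the model.** Taking a screening 2-hour glucose of 200 mg/dl or more as a proxy for the diabetes stratum (an assumption), the reduction over the same grid is 1.3-5.1%. The standard error falls by 1 - sqrt(0.987) = 0.7% to 1 - sqrt(0.949) = 2.6%.

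**5. Cost of the extra covariate.** One of 67 residual degrees of freedom is 1/67 = 1.5%, roughly the variance that a further covariate costs at this sample size. At the bottom of the range in step 4 the net gain is about nil.

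**The case against.** ANCOVA on the baseline value is standard, unbiased and consistent with the primary analysis in Section 9.1. One item on a long secondary list is affected, no sample-size claim rests on it, and every reliability input is assumed. Randomisation is stratified by diabetes (Section 4.5); if the strata enter the model, which Section 9.2 does not say, about half the gain goes. All of this stands. It limits the size of the point but does not remove it.

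Some stronger readings are tempting, and the documents do not support them:

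- *The plan restricts itself to one measurement.* It leaves the baseline value undefined. The loss occurs only if the baseline-visit value alone is used.
- *Fasting glucose and HbA1c are also each measured exactly twice.* For fasting glucose, Section 4.5 implies at least two baseline visits, the OGTT has two samples before the glucose load, and the clamp also follows an overnight fast. There may already be more than one baseline day. For HbA1c, Table 6.2 has no screening column, so its baseline entry is probably, but not certainly, a second sample. The laboratory for the screening HbA1c is not clear either.
- *The gain can be predicted for those two endpoints from their reliability.* At fixed r the gain shrinks as rho rises (step 2). In the simulation it moves the other way: at change SD 15 it is 9.6% with error SD 20 and 5.2% with error SD 35. No gain was calculated for fasting glucose or HbA1c.

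**Conclusion.** The point holds for 2-hour glucose as a minor, optional efficiency gain. Two values exist by design before randomisation, and using both does not bias the arm comparison. The likely size is a 3.5-9.6% reduction in residual variance, or about 1-5% with a diabetes stratum in the model, before the small cost of one degree of freedom. Both ranges rest on assumed within-person variation, assumed individual change and normality; the documents supply only the 140 mg/dl limit and the number of completers.

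For fasting glucose and HbA1c the same step is reasonable, but its benefit is not quantified and may be smaller. A reader might infer that the planned comparisons are biased or that the main result loses power. Neither follows: adjustment for a single baseline value is valid, and the clamp behind both primary endpoints is scheduled only once before randomisation.

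**What to change.** Add to Section 9.2: for 2-hour glucose, the ANCOVA includes the screening value as a second covariate alongside the baseline-visit value. Keep the baseline-visit value as the reference for any reported change, because the screening value was selected by the eligibility limit and will regress towards the mean.

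The sentence may be extended to fasting glucose and HbA1c, after confirming that the HbA1c in the Baseline column of Table 6.2 is a separate sample from the screening one. For these, enter the screening value as a separate covariate and do not average, so that the two values need not come from the same assay or sampling scheme. It would help to state in the same place whether the randomisation strata enter the model, since that changes what the screening value adds.

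The cost is a sentence or two of SAP text and one degree of freedom per model. No new visit, sample or participant is needed. Sections 9.1 and 9.3 need no change.

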#### 2.4.3 Biomarkers

The detailed measures of  $\beta$ -cell function that we will be making provide an opportunity to identify biomarkers that can predict deterioration of  $\beta$ -cell function and/or response to

interventions that can mitigate such deterioration. The identification of such biomarkers is an important ancillary goal of the RISE Consortium. Because of budget constraints, the focus during this stage of the project will be on collecting patient specimens that can used in the future for identification of biomarkers once the main outcomes of the study are known. We will collect samples that can be used to examine previously described peptide markers of diabetes risk (e.g., adiponectin, ferritin, ApoB, C-reactive protein, IL-2 receptor A (34-37) and evolving markers of  $\beta$ -cell mass regulation (e.g., prolactin, DNA fragments and methylation, GLP-1, GIP, HSP90nucleic acids (38-42). We will also collect serum samples that can be analyzed using genomic, micro-RNA, proteomic and metabolomics approaches comparing for example responders to non-responders to the study interventions.

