# **3 STUDY DESIGN**

## 3.1 Overview and Rationale

The BetaFat study protocol described herein will involve 88 adults who are 20 – 65 years old and who have prediabetes or drug-naïve, recent onset and mild type 2 diabetes. Additional inclusion and exclusion criteria are defined below. Participants will be randomized over a 27 month period to either metformin or gastric banding in an open treatment format. The primary outcome will be rate of change in ß-cell compensation for insulin resistance, as defined below. Figure 3 provides an overview of the types and timing of main study procedures.

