# 9.3 Sample Size/Power Calculations

We calculated sample size and power based on practical and statistical considerations. Practically, we can perform surgery on 44 subjects within the time frame and budget of the NIH U01 grant and associated support from Allergan. Allowing loss to follow-up rate of 10% per year, this will give us ~35 subjects per group to complete 24-months follow-up. Statistically, with 35 subjects/group, by using two-group t-test we can detect a minimum effect size of 0.68 in difference between the two intervention groups with type I error of 0.05, 2-sided t-test, and 80% power. Adjustment for baseline value using analysis of covariance will give us 89% power to detect the minimal effect size of 0.68, or give us 80% power to detect a minimal effect size of 0.59 when the baseline and follow-up are correlated with a correlation coefficient of 0.5.

Feasibility of observing this effect size is supported by data from diabetes prevention studies using weight loss, TZDs or metformin, as follows:

- The diabetes risk reduction associated with a mean 12 lb. weight loss in the DPP was 58%, similar to the 55% risk reduction in TRIPOD, where we have direct measures of beta cell function. Those measures revealed an effect size of 0.33 for  $\beta$ -cell compensation between placebo and troglitazone at two years.
- Given the similarity of diabetes risk reduction between TRIPOD and the DPP and assuming mitigation of adverse effects of obesity as a primary mechanism for diabetes prevention in both studies, we estimate an effect size for  $\beta$ -cell compensation of 0.33 for weight loss of ~12 lbs. vs. placebo.
- Gastric band patients at USC had an average weight loss of 35 lbs. at 24-months (Figure 1, above), nearly three times the average weight loss seen over the course of the DPP. Thus, we may see an effect size of 3 x 0.33 = 0.99 for  $\beta$ -cell function in gastric banding compared to no treatment.
- Diabetes risk reduction with metformin in the DPP was 31%, approximately 53% of the reduction seen with lifestyle induced weight loss. If all of the protection were due to preservation of β-cell compensation, this would represent and effect size of ~0.18 vs. placebo.

The differential in projected effect sizes between band-induced weight loss (~0.99) and metformin (~0.18) is ~0.80, well above the 0.68 or the 0.59 minimal effect sizes that we have the power to detect with our study design.

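### The biomarker sets in section 9.2 are chosen and judged in the same 70 to 88 people with no validation, so their fit will be optimistic and a set is likely to look predictive by chance

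*Combined protocol and SAP*

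**What the plan says.** Section 9.2 first plans Pearson and Spearman correlations of each biomarker with measures of β-cell and α-cell function, insulin sensitivity and glucose tolerance. It then says that multiple linear regression models "will be developed to predict measures of glucose metabolism with the most informative biomarker sets". Section 2.4.3 gives the purpose: the study is an opportunity to "identify biomarkers that can predict deterioration" of β-cell function or response to treatment. Aim 3 in section 1.2 relies on regression to find mechanisms and clinical markers.

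The number of candidates is left open. Section 3.3.6 lists C-reactive protein, adiponectin, non-esterified fatty acids and the urine albumin/creatinine ratio, about four in all, and makes further markers depend on funding. Counting everything named in sections 2.4.3 and 3.3.6 gives about 13.

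On numbers of people, the study "will involve 88 adults" (section 3.1), "randomized 1:1 to banding or metformin" (section 4.5). Section 9.3 expects about "35 subjects per group to complete 24-months follow-up".

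No section states a selection rule, an entry threshold, shrinkage, multiplicity control, cross-validation, bootstrap, a hold-out sample or replication for these models. Where section 9.2 speaks of validating, it means OGTT and fasting measures against clamp measures.

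**The concern.** Picking the set that is most informative is a data-driven choice. If the same data then supply its R-squared and p-values, both are biased in favour of the chosen set, because the selection has already used the chance associations. The transformations and nonparametric methods offered at the head of section 9, and the sandwich covariance in section 9.1, deal with distributional assumptions and do not correct this.

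What is at stake is Aim 3. Section 1.3 says that the mediators found will guide later treatment strategies. Markers named with an inflated R-squared may not replicate, and the plan provides no means of telling such a set from a real one.

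**Working it through.** **The plan's own numbers.** Section 9.3 starts from 44 per group: "Allowing loss to follow-up rate of 10% per year" gives 44 × 0.9² = 35.6, or 44 × 0.8 = 35.2, so about 35 per group and 70 in all. With 35 per group the plan says it can "detect a minimum effect size of 0.68 in difference between the two intervention groups", at 80% power and a two-sided 5% level. A noncentral-t calculation gives 80.1%. With baseline adjustment at correlation 0.5 it gives 89.9% power at 0.68 and 80.2% at 0.59, against the stated 89% and 80%. The sample size figures therefore reproduce. They concern the treatment comparison, and the plan gives no figure for the biomarker models.

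**Inputs for the check.** From the plan: n = 70 (88 for a baseline-only model), and 4 or about 13 candidates. Assumed, because the plan is silent: forward selection with entry at p < 0.05 or by AIC, and correlation between markers of 0 to 0.3. No marker has any true association with the outcome.

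**Direct calculation, one outcome.** A false set arises if at least one of k noise markers passes the first entry step. For independent markers with per-marker entry probability a, the chance is about 1 − (1 − a)^k.

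- Entry at p < 0.05: a = 0.05. For k = 4, 1 − 0.95⁴ = 0.185. For k = 13, 1 − 0.95¹³ = 0.487.
- AIC: a marker enters if n × ln(RSS before / RSS after) > 2. At n = 70 this means F > (e^(2/70) − 1) × 68 = 1.97 on 1 and 68 df, so a = 0.165. For k = 4, 1 − 0.835⁴ = 0.514. For k = 13, 1 − 0.835¹³ = 0.904.

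**Simulation, one outcome, n = 70.**

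| Candidates | p < 0.05 entry | AIC |
|---|---|---|
| 4 (marker correlation 0.3) | 0.18 | 0.52 |
| 13 (marker correlation 0 to 0.3) | 0.43-0.48 | 0.85-0.91 |

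The two methods agree. With 13 independent candidates under AIC, the selected set has apparent R-squared 0.125 and R-squared −0.16 in new data. A naive overall F-test of the set has p < 0.05 in 62% of runs.

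**Several outcomes.** Section 9.2 names four families of measures, and sections 3.3.1 to 3.3.5 list many individual ones. The chance of at least one false set (marker correlation 0.3) is:

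| Candidates | Outcomes (correlation) | p < 0.05 entry | AIC |
|---|---|---|---|
| 4 | 4 (0.5) | 0.47 | 0.88 |
| 4 | 20 (0.5 to 0.8) | 0.62-0.87 | 0.95-1.00 |
| 13 | 20 (0.5 to 0.8) | 0.92-1.00 | 1.00 |

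**Does validation cure it?** Pure noise, n = 70, AIC, 250 runs per setting, with the selection repeated inside each fold of 10-fold cross-validation:

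| Candidates | Apparent R² | Cross-validated R² | Permutation test of the whole procedure rejects |
|---|---|---|---|
| 4 | 0.04 | −0.04 | 5.6% |
| 13 | 0.11 | −0.14 | 6.0% |

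The spurious fit disappears, and the permutation test holds about its nominal 5%.

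**A trap in the repair.** If arm and baseline value are forced into the model, its cross-validated R-squared mostly reflects those two terms. In null runs with 10 noise markers, no arm effect and baseline correlation 0.5, a lasso model with both terms forced in had a mean cross-validated R-squared of 0.19. Arm and baseline alone gave 0.18 to 0.19. At least one noise marker was still selected in 22% of runs. Only the increase over the base model says anything about the markers.

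**The case against.** The strongest reply is that the plan commits to very little. Section 2.4.3 calls biomarker identification an ancillary goal and, citing budget, puts the present effort into collecting specimens. Only about four markers are firm. The plan states no stepwise procedure, no fixed set size and no F-test of the chosen set, so every rate above rests on an assumed rule. With four candidates and a p < 0.05 rule, the false-selection rate for one outcome is 18%, well short of certainty. The work is secondary, in what section 9.4 calls a proof-of-principle trial.

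Most of this stands, and it limits the point. A reader might infer that the analysis is bound to report predictive sets from pure noise. The documents do not support that, because they fix neither the candidates nor the rule. A reader might also add the weight, body fat and metabolite exposures to the candidate count. Those belong to a separate analysis in the last paragraph of section 9.2, and candidate counts well above 13 have no basis in the named markers. Nor is the small sample the main cause of false selection: at n = 88 the rates are nearly the same (13 markers at correlation 0.3 under AIC: 0.84). Small n mainly inflates the apparent R-squared.

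The reply does not supply a validation step. Even the most favourable reading, four markers and one outcome, exceeds 5%, and Aim 3 means the results to be used.

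**Conclusion.** The concern holds in a limited form. Choosing and assessing a set in the same people gives an optimistic fit under any data-driven rule. How likely a false set is depends on choices the plan leaves open: the two rules tried span 18% to 52% for one outcome with the four firm markers, and 43% to 91% with all 13, and more outcomes raise these rates. The calculations assume forward selection, marker correlation of 0 to 0.3 and no true associations. They show how easily noise would pass. They do not show that any real association is absent. Nothing here touches the primary treatment comparison or the sample size. This is a cheap improvement to a secondary analysis.

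**What to change.** Before the biomarker data are analysed, add to section 9.2:

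1. The list of candidate biomarkers, the outcomes to be modelled and the selection rule. Stepwise and penalised regression are both acceptable if stated in advance.
2. Repetition of the whole selection, including any tuning, inside cross-validation or bootstrap, with the optimism-corrected R-squared reported in place of the in-sample value.
3. Where arm and baseline value are forced in, the optimism-corrected increase in R-squared over the model with those two terms alone.
4. A permutation test of the whole procedure, and the frequency with which each marker is selected.
5. A statement that the sets are exploratory until replicated.

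The cost is analysis code only: no extra participants, visits or assays. The reported predictive strength will be lower.
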